10.2.2 Infusion-related reactions

Infusion-related reactions are commonly associated with monoclonal antibody infusions and are defined as signs or symptoms with a temporal relationship to the administration of an infusion, occurring typically soon following the start of the infusion, although symptoms may be delayed for up to 24h. They might be limited (skin reaction) or systemic.

From the clinical experience to date, the risk of IRRs associated with emapalumab treatment seems to be very low.

After more than 1000 infusions administered to HLH patients up to the dose of 10 mg/kg, no anaphylactic/anaphylactoid or other significant reactions were observed with emapalumab. IRRs were mainly transient skin reactions observed during and shortly after emapalumab infusions (corresponding to less than 2% of the infusions performed). They resolved spontaneously and did not lead to emapalumab permanent discontinuation.

For more information regarding occurrence of IRRs in completed and ongoing clinical trials with emapalumab, please, refer to the current IB.

10.2.3 Anti-drug antibodies

Occurrence of ADAs inactivating therapeutic effects of the treatment and, in rare cases, inducing adverse reactions, is a potential risk associated with the administration of mAbs. Treatment-emergent ADAs were detected in:

- 1 out of 14 healthy subjects participating in study NI-0501-03; a low titer of ADAs was measured at the last follow-up visit (at week 44 post-emapalumab administration).
- 3 out of 45 patients treated in the context of NI-0501-04/05 studies.
- One patient treated in compassionate use developed transient ADAs.

No adverse events, including decreased efficacy, attributable to antibodies have occurred in these patients.

For more information regarding occurrence of ADAs in completed and ongoing clinical trials with emapalumab, please, refer to the current IB.

10.2.4 Graft versus tumor effect

IFN γ plays a complex role in induction of graft versus tumor effect in recipients of allogeneic hematopoietic stem cell transplantation (21).

The potential effects of emapalumab in patients with hematological or other malignancies undergoing allo HSCT are still unknown. Based on literature evidence, neutralization of IFN γ may adversely affect graft-versus-tumor activity. Therefore, risk minimization measures have been put in place (see Section 10.2.5 below).

For more information regarding malignancy patients treated with emapalumab and ongoing clinical trials with emapalumab, please, refer to the current IB.

10.2.5 Risk minimization measures

In order to ensure safe use of emapalumab in this patient population, the following risk minimization measures will be implemented: stringent exclusion criteria, specific prophylactic treatments, ongoing search for infections caused by relevant pathogens, monitoring for specific AEs, IDMC oversight of patient's safety and comprehensive stopping rules.

All risks mentioned above are considered to be manageable in this patient population, providing that adequate risk mitigation measures are applied to help ensure positive benefit-risk ratio. Risk minimization measures are described below.

10.2.5.1 Measures prior to study enrollment

Prior to enrollment into the study, the following patients will be excluded from participation in the study:

- < 1 year of age (until appropriate dose has been determined).
- With clinically manifested infections caused by Mycobacteria, Salmonella, Histoplasma Capsulatum and HZV prior to HSCT.
- With clinical suspicion of latent tuberculosis.
- Who received BCG vaccine within 3 months prior to HSCT.
- Who received live or attenuated live (other than BCG) vaccine within 6 weeks prior to HSCT.
- With hypersensitivity to emapalumab or any of the excipients.
- With concurrent diseases which may significantly affect the assessment of emapalumab safety or efficacy.
- Pregnant (or planning to become pregnant) or lactating female patients.

10.2.5.2 Measures during the study

The following measures are applied during the monitoring period and treatment with emapalumab:

- Prophylactic use of antivirals for herpes zoster virus.
- Search for pathogens during the study in case of clinical suspicion of infections caused by typical and atypical mycobacteria, salmonella, Histoplasma capsulatum and herpes zoster virus.
- Search for TB at pre-defined time-points..
- Monitoring of re-occurrence of malignant disease by MRD
- Antibodies against emapalumab.
- Pregnancy test for early detection of pregnancy.

- Involvement of IDMC, a group of individuals external to and independent from Sobi AG, investigators and study personnel. An IDMC will review the safety data with the aim to ensure that patients are not exposed to unnecessary risks.
- Appropriate study treatment interruption/discontinuation (see section 11.1) and study stopping rules (see section 11.2).

10.2.6 Benefit-risk evaluation

Based on experience from clinical studies with emapalumab in healthy volunteers and patients with primary and secondary forms of HLH and considering the anticipated benefit and risk minimization measures in place in this protocol, the benefit-risk profile of emapalumab appears to be favorable for its use in patients who are at risk of GF after HSCT.

11 STUDY STOPPING RULES

11.1 Criteria for study treatment interruption/discontinuation

11.1.1 Emapalumab infusion rate decrease /interruption

In case of clinically relevant changes in patient status during emapalumab infusion, the rate of infusion may be decreased or the infusion temporarily interrupted, if deemed necessary by the Investigator and later restarted if patient's situation allows for continuation of the infusion.

11.1.2 Emapalumab permanent discontinuation

Study drug must be permanently discontinued in the following situations:

- Any treatment emergent adverse reaction (i.e. assessed as related), which is considered as life-threatening.
- Any medical condition that the Investigator or Sponsor determines may jeopardize the subject's safety.
- Re-occurrence of malignant disease as judged by the investigator based on clinical assessment including MRD monitoring.

In the situations described above, IDMC will be promptly informed and involved in evaluation of the patient's data.

Other situations that must lead to treatment permanent discontinuation are:

- Pregnancy.
- If a re-transplant is needed based on medical judgment.
- Graft failure.

The reason for study treatment discontinuation should be documented as appropriate in the eCRF.

The Investigator can decide at any time during the study to discontinue the treatment in a patient based on medical judgment, taking into account the benefit/risk ratio for continuing the treatment.

Decision to discontinue treatment will have no impact on the patient's care. All patients who discontinue treatment will be treated according to local medical practice. A subject who prematurely discontinues study treatment is NOT considered as withdrawn from the study. All assessments relevant to EoT visit must be performed and the patient will enter the follow-up period.

11.1.3 Premature withdrawal from the study

Patients (or their legal representative) have the right to voluntarily withdraw consent to participate in the study at any time for any reason. In addition, the Investigator has the right to withdraw a patient from the study at any time, if considered in the best interest of the patient based on medical judgment. Patients should be informed of circumstances under which their participation may be terminated by the Investigator without the patient's consent. Any administrative or other reasons for withdrawal must be explained to the patient.

The reason for study withdrawal should be documented in the eCRF and patient's chart.

In any case, the decision to withdraw or be withdrawn from the study will have no impact on the patient's care and on further treatments administered after withdrawal. Patients who are withdrawn from the study will receive alternative treatments according to the standard of care.

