3.4.5 Follow-Up Period

Assessments to be performed during the follow-up period are detailed in the Schedule of Assessments (Table 7a and Table 7b). The follow-up period will last 3 years from the HSCT date for both patients who received and those who did not receive emapalumab, as detailed below.

Follow-up period: emapalumab treated patients

All emapalumab treated patients will enter the follow-up period:

- (i) Upon completion of treatment or engraftment, whichever comes first
- (ii) In case of premature treatment discontinuation for any reason

The follow-up period for patients who received emapalumab will consist of 6 visits: at 1 week \pm 2 days, 2 weeks \pm 2 days, 4 weeks \pm 2 days, 8 weeks \pm 1 week, 12 weeks \pm 1 week and 24 weeks \pm 2 weeks after last study drug administration (EoS visit) and 3 phone calls for survival observation at 1, 2 and 3 years after HSCT.

During the survival calls defined concomitant medications/procedures (i.e. any HSCT, blood product transfusion, stem cell boost, DLI or hematopoietic agents) and occurrence of GvHD since previous visit/call should be recorded.

The first follow-up visit will be 1 week \pm 2 days after last study drug administration or 1 week after EoT (in case of treatment discontinuation or engraftment before the last dosing day).

Follow-up period: non-emapalumab treated patients

In case treatment with emapalumab has not been initiated, patients will undergo an EoS visit (within 1 week from the last day in the monitoring periods) and enter the phone calls follow-up.

A patient can enter follow-up in the following occasions:

- (i) At the end of the monitoring (Day 42) or extended monitoring (Day 98).
- (ii) If they require a second HSCT anytime during the monitoring periods.
- (iii) If any prohibited medication is taken during the monitoring periods.
- (iv) In case of re-occurrence of malignant disease, GvHD diagnosis, uncontrolled infection or clinical manifestations of infections representing exclusion criteria at time of eligibility to treatment.

The follow-up period for non-emapalumab treated patients will consist of 4 phone calls at 6 months, 1, 2 and 3 years after HSCT. During the survival calls defined concomitant medications/procedures (i.e. any HSCT, blood product transfusion, stem cell boost, DLI or hematopoietic agents) and occurrence of GvHD since previous visit/call should be recorded.

End of Study Visit

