3.4.7 Withdrawal visit

Assessments to be performed during the withdrawal visit are detailed in the Schedule of Assessments (Table 7a and Table 7b). In case of premature withdrawal from the study for any reason (except informed consent withdrawal), patients should undergo a withdrawal visit within 1 week from the date of withdrawal.

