9.3 Pregnancy

Emapalumab treatment must be permanently discontinued in case of pregnancy. The investigator must counsel the subject and discuss the risks of continuing pregnancy and the possible effects on the fetus.

In case of pregnancy, emapalumab treated patients will move to follow-up period. Non-emapalumab treated patients will be withdrawn after performing the EoS/withdrawal visit.

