12.5.6 Handling of missing data

Due to the exploratory nature of the study no imputation of missing data will be performed, all analyses will be based on observed data.

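### After an investigator withdraws a patient, or an untreated patient becomes pregnant, the plan describes no collection of the 3-year outcomes, although consent still stands

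*Combined protocol and SAP*

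**What the plan says.** Section 11.1.3 describes two exits from the study. The patient or representative may withdraw consent. Separately, "the Investigator has the right to withdraw a patient from the study at any time, if considered in the best interest of the patient", and patients are to be told when this may happen without their consent. Section 3.4.7 covers what follows: "In case of premature withdrawal from the study for any reason (except informed consent withdrawal), patients should undergo a withdrawal visit within 1 week". The footnotes to Tables 7a and 7b repeat the rule and place the withdrawal visit in the same column as follow-up visit 6 and the EoS visit.

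Stopping the drug is handled differently. Under section 11.1.2, "The Investigator can decide at any time during the study to discontinue the treatment in a patient based on medical judgment", and "A subject who prematurely discontinues study treatment is NOT considered as withdrawn from the study". Section 3.4.5 lists as a route into follow-up: "In case of premature treatment discontinuation for any reason".

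For pregnancy, section 9.3 moves emapalumab-treated patients to the follow-up period. For the others it says: "Non-emapalumab treated patients will be withdrawn after performing the EoS/withdrawal visit".

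Section 7.1 sets five efficacy endpoints that run to 3 years: overall survival, additional allogeneic HSCT, GvHD, graft support (transfusion for poor graft function, growth factors, stem cell boost or DLI) and event-free engraftment. On missing data, section 12.5.6 rules out imputation and says that "all analyses will be based on observed data".

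**The concern.** After the EoS visit, the 3-year outcomes come from the phone calls in section 3.4.5: at 1, 2 and 3 years for treated patients, and also at 6 months for untreated patients. Study withdrawal is not among the routes into those calls. Followed as written, the plan stops collecting these outcomes in a patient who has not refused anything, and nothing at analysis makes up for it.

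If the reason for withdrawal is related to prognosis, the loss is informative. The selected-dose group is so small that one or two missing patients visibly move a reported proportion. The loss is avoidable at the point of collection and cannot be repaired afterwards.

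**Working it through.** **Step 1. Set the exits side by side.**

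| Event | Where stated | What follows |
|---|---|---|
| Drug stopped for any reason, including graft failure, re-transplant or recurrence of malignancy | 11.1.2, 3.4.5 | Follow-up visits and calls to 3 years |
| Untreated: second HSCT or prohibited medication during monitoring | 3.4.5 | EoS visit, then calls to 3 years |
| Untreated: recurrence, GvHD or listed infection when treatment would start | 3.4.3, 3.4.5 | Calls to 3 years |
| Pregnancy, treated | 9.3 | Follow-up period |
| Pregnancy, untreated | 9.3 | EoS/withdrawal visit, then withdrawn |
| Investigator withdraws patient from study | 11.1.3, 3.4.7 | Withdrawal visit; nothing further described |

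Only the last two rows end outcome collection without the patient withdrawing consent.

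**Step 2. What is still captured.** The column shared with the EoS visit records GvHD, graft failure and graft rejection up to the withdrawal visit. Sections 9.1.4 and 9.2.2 follow AEs and SAEs ongoing at the EoS visit, SAEs through to an outcome such as death. Sections 9.3.1 and 9.3.2 require pregnancies up to EoS to be reported and their outcome collected. None of this is planned collection of new deaths, second transplants, GvHD or graft support up to 3 years.

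**Step 3. Group sizes.** The plan gives no withdrawal rate and no figure for this loss, so there is nothing of its own to reproduce on the point itself. From sections 12.1 and 12.2:
- Selected dose: 4 + 6 = 10 evaluable patients at most.
- All cohorts: 3 × 4 + 6 = 18 evaluable patients treated for primary GF.
- Included: about 250 at most, so up to 250 − 18 = 232 who are not among those 18. The number never treated is smaller, because non-evaluable and secondary-GF patients also receive drug.

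**Step 4. Effect of losing patients.** Each lost patient has one of two outcomes for any yes/no endpoint, so the best/worst-case range is w/n for w lost of n. With n = 10, one lost patient gives 1/10 = 10 points and two give 20 points.

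Illustration, assuming true 3-year survival of 6/10 = 60% (exact 95% CI 26 to 88%) and that lost patients leave the denominator:

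| Lost | All lost patients die | All lost patients survive |
|---|---|---|
| 1 | 6/9 = 67% | 5/9 = 56% |
| 2 | 6/8 = 75% (exact 95% CI 35 to 97%) | 4/8 = 50% |

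The shift is +7 or +15 points in one direction and −4 or −10 in the other.

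**Step 5. How likely is at least one loss among 10?** With an assumed per-patient withdrawal rate r, the chance is 1 − (1 − r)^10: 18% at r = 2%, 40% at 5% and 65% at 10%. These rates are assumptions; the documents give none.

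**The case against.** A reader might infer that investigator withdrawal removes the patients who are doing badly, so that reported outcomes look better than they are. The documents do not support that as a fact. Section 11.1.2 sends graft failure, need for re-transplant, recurrence of malignancy and any condition that jeopardises safety to drug discontinuation with follow-up, and section 3.4.5 keeps most of the comparable untreated cases. Investigator withdrawal is what remains after those routes. Its rate and reasons are not given, and pregnancy is not a marker of a failing graft.

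A reader might also infer that stopping the drug alone would always meet the same clinical need. That holds at most for patients on emapalumab. Most included patients are only monitored, and treated patients in follow-up have finished dosing. For them, withdrawal relieves visits and blood sampling.

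Nor does the plan say that all contact ends. The gap is read from silence, and the follow-up of AEs, SAEs and pregnancy continues as set out above. Observed-data analysis is also compatible with censoring at last contact, and section 12.5 leaves full methods to the SAP, so dropping lost patients from the denominator is an assumption.

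Finally, the stakes are limited. All analyses are exploratory, the main efficacy endpoint is primary GF up to end of treatment, the interim rules count GF after completed treatment, and the illustrated shifts lie well inside an interval of 26 to 88%.

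All of this stands, and it limits the point to an improvement. It does not supply the missing outcomes: no section carries the calls past an investigator withdrawal, and censoring does not recover events that were never collected.

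**Conclusion.** The point holds as a cheap improvement. Followed as written, sections 11.1.3, 3.4.7 and 9.3 leave the five 3-year endpoints without planned collection after an investigator withdrawal or a pregnancy in an untreated patient. This is inconsistent with how the plan treats drug discontinuation, second HSCT, prohibited medication and pregnancy in treated patients.

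The size is 10 percentage points of best/worst-case range per lost patient, given about 10 patients at the selected dose. The direction and actual amount of bias are unknown. The survival figures are illustrations that rest on an assumed 6/10 survivors and on lost patients being dropped. The dose decision, the main efficacy endpoint and the interim stopping guidance are little affected.

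**What to change.** In sections 11.1.3, 3.4.7, 3.4.5 and 9.3, state that an investigator's decision to withdraw a patient, or pregnancy in an untreated patient, ends study visits and procedures only. The section 3.4.5 phone calls then continue unless the patient or representative withdraws consent for follow-up. A permitted record check of vital status, HSCT, GvHD and graft support could replace the calls. Add study withdrawal to the routes into follow-up in section 3.4.5. As an option at the analysis stage, report best/worst-case bounds for any patient still lost.

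The cost is protocol and consent-form wording and up to 3 calls (treated) or 4 calls (untreated) per affected patient. There are no extra visits or samples, and neither the sample size nor clinical management changes.

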11.1.4 Non-evaluable patients

The following cases represent non-evaluable patients when treated for primary GF:

- Administration of any prohibited medication during treatment.
- Premature treatment withdrawal for reasons other than safety or lack of efficacy.
- More than 1 infusion missed.

- Documented delay of treatment initiation by more than 36 hours after CXCL9 sample collection time and levels above threshold.

Recruitment of patients treated for primary GF will continue until the required number of evaluable patients for each interim analysis and final analysis is met.

This definition of non-evaluable patients does not apply for patients treated for secondary GF.

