3.4.4 Treatment Period

Assessments to be performed during the treatment period are detailed in the Schedule of Assessments (Table 6a and Table 6b).

Criteria to enter treatment during the monitoring and extended monitoring period, and not to start treatment, are defined in section 3.4.3.

- Patients treated for primary or secondary GF will receive emapalumab for maximum 15 infusions or until engraftment is confirmed.
- Engraftment is defined as ANC \geq 500 cells/ μ L for 3 consecutive measures and donor chimerism above 60% (for primary GF) or ANC \geq 500 cells/ μ L for 3 consecutive measures and 2 consecutive measures of donor chimerism above 60% or 7 days of platelets above 20000 cells/ μ L without transfusion (for secondary GF).
- Preferably, ANC recovery should be based upon three consecutive laboratory values (ANC sample drawn 1 or 2 days apart maximum).
- Patients must be hospitalized in case of active infections requiring IV antimicrobial therapy during treatment.
- If engraftment is confirmed prior to the last dosing day (dose 15) or if patients discontinue treatment, patients will perform all assessments as per end of treatment visit (EoT) and can be discharged if hospitalized provided that there is no active infections requiring IV antimicrobial therapy.
- Patients who take prohibited medications will not be discontinued from emapalumab treatment unless for medical reasons.
- Pre-emptive treatment for secondary GF is optional and it is investigator's responsibility to decide whether to start pre-emptive treatment with emapalumab or not.

End of Treatment (EoT) visit

Assessments to be performed during the EoT visit are detailed in the Schedule of Assessments (Table 6a and Table 6b).

Patients who discontinue treatment or engraft before the last dosing day (dose 15) will attend the EoT visit. Patients who complete treatment until dose 15 will not be required to undergo an EoT visit.

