6.2 Authorized treatments

The following treatments are allowed during the study:

- Prophylaxis and therapy of infections (antibiotics, antifungal and anti-viral) as per local medical practice.
- Conditioning (myeloablative conditioning [MAC], RIC or NMA) prior to HSCT as per local medical practice.
- GvHD prophylaxis and treatment as per local medical practice..
- Steroids during monitoring, extended monitoring and follow up.
- During emapalumab treatment only topical steroids are allowed and methylprednisolone up to 2 mg/kg/day (or other equivalent steroid dose) for not more than 2 days.
- Hematopoietic growth factors, stem cell boost, donor lymphocyte infusion (DLI).
- Intravenous immunoglobulin (IVIG) is only allowed as replacement treatment (i.e. not at doses expected to produce an immunomodulatory effect) based on medical judgment.
- Analgesic treatment, transfusion of blood products, electrolyte and glucose infusions, IV parenteral nutrition, inotropic support, ultrafiltration or hemodialysis.

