12.4 Definition of study populations

The following analysis sets/populations will be used:

- All included population: This population will comprise all patients included in the study whether they are treated or not and will be used for presenting safety endpoints.
- All treated population: This population will comprise all patients who received at least one dose of investigational product and will be used for presenting efficacy endpoints.
- All evaluable population: This population will comprise all patients treated for primary GF who have:
 - No administration of any prohibited medication during treatment.
 - No premature treatment withdrawal for reasons other than safety or lack of efficacy.
 - Not more than 1 infusion missed.
 - No delay of treatment initiation (more than 36 hours from CXCL9 sample collection time with levels above threshold).

This population is the primary analysis population for determination of the appropriate dose regimen and to assess efficacy of emapalumab in pre-empting primary graft failure.

- Per protocol population: This population includes all evaluable patients without major protocol deviations. A major protocol deviation is here defined as a deviation that has been classified as major based on that it might influence the primary efficacy endpoint (pre-emption of GF). The per protocol population will be used to assess the appropriate dose regimen and efficacy of emapalumab in pre-empting primary GF.
- PK/PD population: This population will comprise all patients included in the study treated with emapalumab and with at least one post-dose PK sample. The PK/PD population will be used for presenting PK/PD endpoints.

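### Two evaluability criteria can take an observed on-treatment graft failure out of the futility and success counts in section 12.2

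*Combined protocol and SAP*

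**What the plan says.** The synopsis and sections 11.1.4 and 12.4 give the same four evaluability criteria for patients treated for primary GF. Three concern events after dosing starts: "Administration of any prohibited medication during treatment"; "Premature treatment withdrawal for reasons other than safety or lack of efficacy"; and "More than 1 infusion missed". The fourth is a treatment start more than 36 hours after the qualifying CXCL9 sample. Only the withdrawal criterion has an exception based on the reason. Section 12.4 restates the four as conditions that must all hold, including "No premature treatment withdrawal for reasons other than safety or lack of efficacy".

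On the role of this set, section 12.4 says: "This population is the primary analysis population for determination of the appropriate dose regimen". It also names the set for assessing efficacy against primary GF. Non-evaluable patients are in effect replaced: "Recruitment of patients treated for primary GF will continue until the required number of evaluable patients for each interim analysis and final analysis is met".

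Section 3.4.4 adds: "Patients who take prohibited medications will not be discontinued from emapalumab treatment unless for medical reasons". The graft outcome of such a patient is therefore normally still observed.

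Section 12.2 applies its guidance to evaluable patients in the selected-dose cohort:

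- At 4 patients, 3 or more GF means stop for futility.
- At 7 patients, 5 or more GF means stop for futility, and 0 or 1 allows a stop for success.

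The main efficacy endpoint in section 7 is primary GF between start and end of treatment.

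**The concern.** The withdrawal criterion shows that the sponsor saw the danger of excluding patients for reasons tied to outcome. It guards one of the three post-dosing routes out of the set. The other two can also be linked to a deteriorating course. A patient who receives a kinase inhibitor, a biologic outside the rituximab exception, or steroids beyond the section 6.3 limit may continue emapalumab and later have primary GF. So may a patient who misses two infusions because of a serious infection. In both cases the failure is seen but does not enter the section 12.2 count, and a new patient fills the place. Had the second patient been withdrawn for that same infection, the existing exception would have kept the patient in.

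There is also a gap in wording. The plan does not define a missed infusion, and section 12.4 requires all four conditions. Section 11.1.2 makes graft failure a reason for permanent discontinuation. If that happens after dose 5, then 15 − 5 = 10 planned doses are not given. Read literally, the missed-infusion criterion would remove the patient whom the lack-of-efficacy exception is meant to keep. That is not the natural reading, but nothing excludes it.

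At stake is a decision taken on 4 or 7 patients, where one or two exclusions can change the outcome.

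**Working it through.** **The plan's own figures (section 12.1).** Monitored patients needed to treat 4, at trigger rates of 30% and 10%: 4/0.30 = 13.3, so 14 (stated 15), and 4/0.10 = 40 (stated 40). The evaluable maximum is 3 × 4 + 6 = 18. At a 10% trigger rate that needs 18/0.10 = 180 monitored. The stated maximum of about 250 equals 180/(1 − 0.28), that is 250 × 0.10 = 25 treated for 18 evaluable. A 28% non-evaluable allowance is an inference; the plan does not state one. It gives no reference GF rate and no error rates, so there is no operating characteristic to reproduce.

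**Stopping guidance.** Let q be the GF rate among evaluable patients, with stages of 4 and then 3 more.

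- Futility at 4: 4q³(1 − q) + q⁴.
- Futility at 7, having passed the first look: 2 of 4, then 3 of 3, that is 6q²(1 − q)² × q³.
- Success at 7: (1 − q)⁷ + 7q(1 − q)⁶.

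At q = 0.50, futility is 5/16 + 6/128 = 0.3125 + 0.0469 = 35.9%, and success is 8/128 = 6.2%.

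**Selective removal.** Let p be the true GF rate in treated patients and r the share of failing patients made non-evaluable, with no GF-free patients removed. Then q = p(1 − r)/[p(1 − r) + (1 − p)]. At p = 0.50, r = 10% gives 0.45/0.95 = 0.474, and r = 25% gives 0.375/0.875 = 0.429. Both p and r are assumptions. Cells show P(success stop) / P(futility stop):

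| True GF rate | r = 0 | r = 10% | r = 25% |
|---|---|---|---|
| 40% | 15.9% / 20.1% | 19.4% / 16.9% | 26.3% / 12.2% |
| 50% | 6.2% / 35.9% | 8.2% / 31.4% | 12.4% / 24.2% |
| 60% | 1.9% / 55.0% | 2.6% / 50.0% | 4.5% / 41.3% |

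**Removal of successes too.** At p = 0.50, with 25% of failures and 10% of successes removed, q = 0.375/(0.375 + 0.45) = 0.455 and P(success stop) is about 10%, against 12.4% when only failures are removed. With equal shares, q = p and there is no shift.

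**Single-trial example.** Nine patients are treated for primary GF and 3 fail. Two of the 3 had a prohibited drug or missed two infusions. The evaluable count is 1/7 (14%), which meets the success rule. Among all treated it is 3/9 (33%).

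**The case against.** A reader might infer that any patient rescued for a failing graft leaves the count, or that rescue is never held against the drug. The documents do not support either. Section 6.2 authorizes growth factors, stem cell boost and DLI, so these do not affect evaluability. Graft failure or the need for re-transplant forces discontinuation under section 11.1.2, which is naturally read as withdrawal for lack of efficacy and so stays evaluable. Section 7.1 lists graft-support treatment, additional HSCT, poor graft function and event-free engraftment as efficacy endpoints. Whether a boost or DLI should count as failure is a choice of endpoint, not a fault in evaluability.

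Nothing in the protocol says that prohibited drugs are used to rescue grafts. Section 10.1 gives a second transplant as the only treatment once GF is confirmed. Breaches may be unrelated to the graft, and a patient who misses two doses for infection is not thereby a graft failure. The removal shares have no source in the documents, and the model above takes out failures only.

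The counts also carry limited weight. Section 12.2 calls them guidance and says the study can, not must, stop for success. They apply after the dose has been chosen on PK/PD data. All analyses are exploratory (section 12.5), the IDMC and sponsor review benefit-risk, and efficacy is also presented for all treated patients (section 12.4). Excluding patients on other cytokine-active drugs is reasonable for PK/PD.

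All of this stands and limits the size of the point. It does not close the gap: the written counts use evaluable patients only, the all-treated display does not feed them, and the per-protocol set is a subset of the evaluable set and so restores nobody.

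**Conclusion.** The point holds in a narrow form. A patient who, while still on emapalumab, receives a prohibited drug or misses more than one infusion and then has primary GF is left out of the 4- and 7-patient counts and replaced. If such events are more frequent in failing patients, the evaluable GF rate could be biased down, with too few futility stops and too many success stops.

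At a true GF rate of 50%, the chance of meeting the success rule rises by 2 percentage points if 10% of failures are lost, and roughly doubles if 25% are. These figures rest on assumed removal shares with no successes removed; they illustrate sensitivity and do not estimate the actual bias. The direction depends on failures being removed more often than successes, which the documents neither show nor exclude. Because the analyses are exploratory and the counts are guidance, this is a should-fix point, best settled before the next interim count.

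**What to change.** In section 11.1.4, section 12.4 and the synopsis, state that:

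- for the efficacy count, any primary GF observed from start to end of treatment is a failure, whatever prohibited medication was given or infusions were missed;
- the existing exception for safety or lack of efficacy also applies to the prohibited-medication and missed-infusion criteria;
- doses not given after permanent discontinuation are not missed infusions.

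In section 12.2, show the futility and success counts also over all patients treated for primary GF. Call success only if that count does not contradict it, and define beforehand what would contradict it. This second count matters for another reason. Keeping every failure while still dropping some GF-free patients tilts the evaluable rate the other way: at p = 0.50 with 10% of successes dropped, q = 0.50/(0.50 + 0.45) = 0.526. The all-treated count drops nobody and so checks both directions.

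The cost is wording and one eCRF field for the reason a prohibited drug was given or an infusion missed. That reason comes from an open-label investigator, which is why the first bullet does not depend on it. Fewer replacements would be needed. Some evaluable patients would have confounded PK/PD data, which can be flagged or cut at the date of the prohibited drug. The change concerns scoring only; the lists of authorized and prohibited treatments stay as they are.
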